10.7.2 Intraocular Pressure (IOP)

IOP - Intraocular pressure and change in intraocular pressure will be summarized descriptively by time point.

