3.2.2 Safety Endpoints

The primary goal of the study is to evaluate the safety and tolerability of jCell injection: The criteria that will be used to establish safety include:

- Slit-lamp findings, i.e., anterior chamber cell or flare; acute cataract development or progression in phakic patients, vitreous haze.
- Absence of tumor formation, overt immune rejection, decrease in BCVA attributable to treatment
- Absence of clinically significant, persistent increase in intraocular pressure (>10 mm Hg above baseline or IOP > 25 mm Hg), clinically significant epiretinal membrane, retinal detachment, neovascularization, or endophthalmitis
- No clinically significant adverse events attributable to investigational product (jCell) injection
- Patient comfort (no intolerable pain related to procedure)

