No	n (%)	n (%)	n (%)	n (%)	n (%)
Any Dose interruptions?					
Yes	n (%)	n (%)	n (%)	n (%)	n (%)
No	n (%)	n (%)	n (%)	n (%)	n (%)
Were any Adverse Events observed?					
Yes	n (%)	n (%)	n (%)	n (%)	n (%)
No	n (%)	n (%)	n (%)	n (%)	n (%)
Subject Vital Signs comparable to pre injection levels?					
Yes	n (%)	n (%)	n (%)	n (%)	n (%)
No	n (%)	n (%)	n (%)	n (%)	n (%)
Subject IOP < 30mm post treatment of injection?					
Yes	n (%)	n (%)	n (%)	n (%)	n (%)
No	n (%)	n (%)	n (%)	n (%)	n (%)
Subject Prescribed Topical Treatment after Study Drug					
Yes	n (%)	n (%)	n (%)	n (%)	n (%)
No	n (%)	n (%)	n (%)	n (%)	n (%)
cludes both Cohorts 1 and 2.					
gram.sas date time					

	Safety PopulationSafety PopulationCohort 1Cohort 2Class / rm $(N=)$ $(0.5 x 10^6 hRPC$ $(N=)$ $(N=)$ Total [1] $(N=)$ SubjectsEventsSubjectsEventsSubjectsEventsSubjectsEventsSubjectsEventsSubjectsEventsSubjectsEventsSubjectsEventsSubjectsEventsrting at Least One TEAEn (%)xxn (%)<									
		Coh	ort 1			Coh	ort2			
System Organ Class /	0.5 x 10	⁶ hRPC			0.5 x 10 ⁶	hRPC			Tota	ıl ^[1]
Preferred Term	(N=	=)	(N	=)	(N=	=)	(N	J=)	(N	=)
	Subjects	Events	Subjects	Events	Subjects	Events	Subjects	Events	Subjects	Events
Subjects Reporting at Least One TEAE	n (%)	XX	n (%)	XX	n (%)	XX	n (%)	XX	n (%)	xx
System Organ Class 1	n (%)	XX	n (%)	XX	n (%)	XX	n (%)	XX	n (%)	XX
Preferred Term 1	n (%)	XX	n (%)	XX	n (%)	XX	n (%)	XX	n (%)	XX
Preferred Term 2	n (%)	XX	n (%)	XX	n (%)	XX	n (%)	XX	n (%)	XX
System Organ Class 2	n (%)	XX	n (%)	xx	n (%)	XX	n (%)	XX	n (%)	XX
Preferred Term 1	n (%)	XX	n (%)	XX	n (%)	XX	n (%)	XX	n (%)	XX
Preferred Term 2	n (%)	XX	n (%)	XX	n (%)	XX	n (%)	XX	n (%)	XX

Table 14.3.1.1TEAEs by System Organ Class and Preferred TermSafety Population

^[1] Total includes both Cohorts 1 and 2.

...

Note: At each level of summation (overall, system organ class, preferred term), subjects reporting more than one adverse event are counted only once. path/t_program.sas date time

Table 14.3.1.2 TEAEs by System Organ Class, Preferred Term and Maximum Severity Safety Population

				Coh	nort 1			
System Organ Class /		0.5	x 10 ⁶ hRPC (N=)					
Preferred Term	Mild	Moderate	Severe	Life Threatening	Mild	Moderate	Severe	Life Threatening
Subjects Reporting at Least One TEAE	n (%)	n (%)	n (%)	n (%)	n (%)	n (%)	n (%)	n (%)
System Organ Class 1	n (%)	n (%)	n (%)	n (%)	n (%)	n (%)	n (%)	n (%)
Preferred Term 1	n (%)	n (%)	n (%)	n (%)	n (%)	n (%)	n (%)	n (%)
Preferred Term 2	n (%)	n (%)	n (%)	n (%)	n (%)	n (%)	n (%)	n (%)

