Mean (SD)	xx.x (xx.x)	xx.x (xx.x)	xx.x (xx.x)	xx.x (xx.x)	xx.x (xx.x)	
Median	XX.X	XX.X	XX.X	XX.X	XX.X	
Min, Max	XX, XX	XX, XX	XX, XX	XX, XX	XX, XX	
Day 1						
n	n	n	n	n	n	
Mean (SD)	xx.x (xx.x)	xx.x (xx.x)	xx.x (xx.x)	xx.x (xx.x)	xx.x (xx.x)	
Median	XX.X	XX.X	XX.X	XX.X	XX.X	
Min, Max	XX, XX	XX, XX	XX, XX	XX, XX	XX, XX	
Day 1 Change from Baseline						
n	n	n	n	n	n	
Mean (SD)	xx.x (xx.x)	xx.x (xx.x)	xx.x (xx.x)	xx.x (xx.x)	xx.x (xx.x)	
Median	XX.X	XX.X	XX.X	XX.X	XX.X	
Min, Max	XX, XX	XX, XX	XX, XX	XX, XX	XX, XX	
Day 2						
n	n	n	n	n	n	
Mean (SD)	xx.x (xx.x)	xx.x (xx.x)	xx.x (xx.x)	xx.x (xx.x)	xx.x (xx.x)	
Median	XX.X	XX.X	XX.X	XX.X	XX.X	
Min, Max	XX, XX	XX, XX	XX, XX	XX, XX	XX, XX	

Table 14.3.4.8.1 Intraocular Pressure (IOP): Study Eye Safety Population

^[1] Total includes both Cohorts 1 and 2.

^[2] Baseline is defined as the value obtained at the baseline visit. If the baseline value is missing, the baseline value will be the last non-missing value recorded prior to the first dose of study drug. path/t_program.sas date time

Programmer Note: Continue table for Visits: Day 3, Day 7, Day14, Day 21, Day 28, Month 2, Month 3, Month 4, Month 5, Month 6, Month 9, Month 12/Early Term. Programmer Note: Table 14.3.4.8.2 will contain the same information for the Non-Study Eye.

Table 14.3.4.9.1 **B-Scan: Study Eye** Safety Population

	Cohor	t 1	Cohort 2			
	0.5 x 10 ⁶ hRPC		0.5 x 10 ⁶ hRPC		Total ^[1]	
	(N=)		(N=)		(N=)	
Baseline ^[2]	(n=)	(n=)	(n=)	(n=)	(n=)	
Normal	n (%)	n (%)	n (%)	n (%)	n (%)	
Abnormal, Not Clinically Significant	n (%)	n (%)	n (%)	n (%)	n (%)	
Abnormal, Clinically Significant	n (%)	n (%)	n (%)	n (%)	n (%)	
Good	n (%)	n (%)	n (%)	n (%)	n (%)	
Poor	n (%)	n (%)	n (%)	n (%)	n (%)	
Injected Cells Visualized						
Yes	n (%)	n (%)	n (%)	n (%)	n (%)	
No	n (%)	n (%)	n (%)	n (%)	n (%)	
Not Applicable	n (%)	n (%)	n (%)	n (%)	n (%)	
Day 3	(n=)	(n=)	(n=)	(n=)	(n=)	
Normal	n (%)	n (%)	n (%)	n (%)	n (%)	
Abnormal, Not Clinically Significant	n (%)	n (%)	n (%)	n (%)	n (%)	
Abnormal, Clinically Significant	n (%)	n (%)	n (%)	n (%)	n (%)	
Good	n (%)	n (%)	n (%)	n (%)	n (%)	
Poor	n (%)	n (%)	n (%)	n (%)	n (%)	
Injected Cells Visualized						
Yes	n (%)	n (%)	n (%)	n (%)	n (%)	
No	n (%)	n (%)	n (%)	n (%)	n (%)	
Not Applicable	n (%)	n (%)	n (%)	n (%)	n (%)	
des both Cohorts 1 and 2.						

^[2] Baseline is defined as the value obtained at the baseline visit.

path\t_program.sas date time

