	xxx-xxx	Baseline	Date9.(xx)	Abnormal NCS	Yes	Abnormal NCS	Yes

Cohort 2 - 0.5 x 10⁶ hRPC xxx--xxx Screening Date9.(xx)

Note: CS=Clinically Significant, NCS=Not Clinically Significant.

path\l_program.sas date time

Programmer Note: If Fundus Photography was not performed, please display "Not Done" and the reason in the "Date Performed" column.

Page 1 of x

Listing 16.2.8.16 Intraocular Pressure (IOP)

			Measurement								
	Subject		Date (Study	Measurement	Was a Tonopen	If No, Specify Device	OD (Right)	OS (Left)			
Treatment Group	ID	Visit	Day)	Time	Used?	Used	Mean IOP (mmHg)	Mean IOP (mmHg)			
Cohort 1 - 0.5 x 10 ⁶ hRPC	xxxxxx	Baseline	Date9.(xx)	Time5.	Yes/No	xxxxxxxx	xx	XX			
		Day 0	Not done: Reason								
		Dayl	Date9.(xx)	Time5.	Yes/No	XXXXXXXXX	XX	XX			
		Day 2	Date9.(xx)	Time5.	Yes/No	XXXXXXXXX	XX	XX			
		Day 3	Date9.(xx)	Time5.	Yes/No	XXXXXXXXX	XX	XX			
		Day 7	Date9.(xx)	Time5.	Yes/No	XXXXXXXXX	XX	XX			
		Day 14	Date9.(xx)	Time5.	Yes/No	XXXXXXXXX	XX	XX			
		Day 21	Date9.(xx)	Time5.	Yes/No	XXXXXXXXX	XX	XX			
		Day 28	Date9.(xx)	Time5.	Yes/No	XXXXXXXXX	XX	XX			
		Month 2	Date9.(xx)	Time5.	Yes/No	XXXXXXXXX	XX	XX			
		Month 3	Date9.(xx)	Time5.	Yes/No	XXXXXXXXX	XX	XX			
		Month 4	Date9.(xx)	Time5.	Yes/No	XXXXXXXXX	XX	XX			
		Month 5	Date9.(xx)	Time5.	Yes/No	XXXXXXXXX	XX	XX			
		Month 6	Date9.(xx)	Time5.	Yes/No	XXXXXXXXX	XX	XX			
		Month 9	Date9.(xx)	Time5.	Yes/No	XXXXXXXXX	XX	XX			
		Month 12 or Early Termination	Date9.(xx)	Time5.	Yes/No	XXXXXXXXX	XX	XX			

Cohort 2 - 0.5 x 10⁶ hRPC xxx--xxx Baseline Date9.(xx)

path\l_program.sas date time

Programmer Note If an IOP measurement was not completed, please display "Not Done" and the reason in the "Measurement Date/Time" column.

Listing 16.2.8.17 B-Scan

			Study Eye					Right Eye (OD)				Left Eye (OS)		
			Measurem		Injected Cells			Abnormal,				Abnormal,		
Treatment Group	Subject ID	Visit	ent Date (Study Day)	Time	Visualized?if Yes, Description	Video Taken?	B-Scan Result	Change from Previous Visit?	Pathology Result Observed	Overall Pathology Result	B-Scan Result	Change from Previous Visit?	Pathology Result Observed	Overall Pathology Result
Cohort 1 - 0.5 x 10 ⁶ hRPC	xxxxxx	Baseline	Date9.(xx)	Time5.	Yes: Description/ No/NA	Yes/No/NA	Normal	Yes/No/NA	Retinal Detachment	Good/Poor	Normal	Yes/No/NA	Retinal Detachment	Good/Poor
		Day 3	Not done: Reason											

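### The SAP plans no count of eyes meeting the protocol's intraocular pressure safety criterion, and its by-visit tables cannot show whether a rise persisted in the same eye

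*SAP*

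**What the plan says.** Safety and tolerability are the primary objective (Protocol 2.1, SAP 2.1). Protocol 3.2.2 lists the criteria by which safety is to be established. One of them is "Absence of clinically significant, persistent increase in intraocular pressure (>10 mm Hg above baseline or IOP > 25 mm Hg", and it is the only item in that list with numeric limits. The documents do not say how long a rise must last to count as persistent.

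SAP 10.7.2 consists of one sentence: "Intraocular pressure and change in intraocular pressure will be summarized descriptively by time point". The shell for Table 14.3.4.8.1 (study eye; Table 14.3.4.8.2 repeats it for the non-study eye) has n, mean (SD), median, minimum and maximum. It opens with baseline, passes to Day 1 and "Day 1 Change from Baseline", then Day 2, and its programmer note runs on: "Continue table for Visits: Day 3, Day 7, Day14, Day 21, Day 28, Month 2, Month 3", and so to Month 12. It has no Day 0 block and no row for either limit.

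Day 0 pressure after injection is collected (Protocol 7.4 and Table 2). In the SAP tables it appears only in Table 14.3.1, as a Yes/No item: "Subject IOP < 30mm post treatment of injection". Listing 16.2.8.16 prints the right-eye and left-eye pressure of each subject at baseline, Day 0 and the later visits.

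**The concern.** The protocol's criterion concerns individual eyes followed over time: did this eye exceed a limit, and did it stay there? The planned tables describe all eyes in a column, one visit at a time, so the link between one visit and the next within an eye is lost. A report built from them would state a distribution of pressures at each visit but not the number of eyes meeting a criterion that the protocol uses to establish safety.

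The remaining route is to read the listing by eye. Without a definition of *persistent* fixed in advance, that reading would depend on a choice made with the data in view. SAP section 5 treats only the analyses described in the plan as a priori and requires anything else to be labelled post hoc. A later count for this criterion would carry that label.

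**Working it through.** The plan has no figure to reproduce here: SAP section 4 states that the sample size had no formal statistical basis, and neither document gives an expected number of pressure events. The check compares what the criterion needs with what the tables hold.

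**Inputs.** Limits: change >10 mm Hg or value >25 mm Hg (Protocol 3.2.2). Cell sizes: 4, 4, 3 and 3 eyes by dose within each cohort, up to 28 in total (Protocol synopsis and 3.1). Statistics: n, mean, SD, median, minimum, maximum (SAP Appendix C). Assumed for the checks: whole-number readings between 8 and 35 mm Hg.

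**1. What one visit's table reveals.** Take four eyes with baseline 15, one of which rises to 29.
- Mean change = 14/4 = +3.5, and mean IOP = (15 + 15 + 15 + 29)/4 = 18.5.
- Over 28 eyes, with the others unchanged, mean change = 14/28 = +0.5.
- The maximum reads 29, and the maximum change reads +14.

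The mean is diluted, but the maximum shows that both limits were crossed. In a 3-eye cell the minimum, median and maximum are the three readings themselves. In a 4-eye cell, enumerating all 31,465 possible sets of readings gives 0 ambiguous sets if the SD has two decimals. With the SD to one decimal, as the shell displays it, 3,370 are ambiguous, and 328 of these leave the number of eyes above 25 uncertain. Within one visit and one dose column, therefore, little is lost.

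**2. What the tables reveal across visits.** Take four eyes, all with baseline 15, at four visits.

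| Eye | Set 1 | Set 2 |
|---|---|---|
| A | 28, 28, 28, 28 | 28, 15, 16, 14 |
| B | 15, 15, 15, 15 | 15, 28, 14, 16 |
| C | 16, 16, 16, 16 | 16, 14, 28, 15 |
| D | 14, 14, 14, 14 | 14, 16, 15, 28 |

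At every visit in both sets the four readings are 14, 15, 16 and 28:
- mean = 73/4 = 18.25, SD = √(128.75/3) = 6.55, median 15.5, minimum 14, maximum 28
- change: mean +3.25, SD 6.55, minimum −1, maximum +13

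The printed tables are identical. Counting eyes over a limit at any visit gives 1 in Set 1 and 4 in Set 2. Counting eyes over a limit at two or more consecutive visits (used here only as an illustration) gives 1 in Set 1 and 0 in Set 2.

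**3. Day 0.** A post-injection reading of 26 to 29 mm Hg is above 25 but below 30. It is a Yes in Table 14.3.1 and appears in no other table. It is visible only in the listing.

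**4. The SAP's own practice.** For visual acuity, SAP 9.1 and Tables 14.2.1.3 and 14.2.1.4 count subjects with gains of at least 5, 10 and 15 letters at any post-baseline assessment and at Months 3, 6, 9 and 12. The same kind of any-visit threshold count is missing for the pressure criterion.

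**5. What a count could support.** With no eye affected, the exact one-sided 95% upper limit is 1 − 0.05^(1/n): 10.1% for 0/28, 19.3% for 0/14, 52.7% for 0/4 and 63.2% for 0/3.

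**The case against.** The strongest reply is that nothing is hidden. Listing 16.2.8.16 gives each eye's pressure over time, Day 0 included, and with at most 28 subjects a reader can follow every one. The maximum exposes any crossing at a tabulated visit. If no maximum exceeds a limit, the tables show from Day 1 on that no eye met it. A clinically significant rise also fits the adverse event definition in Protocol 9.1, so it could be counted by dose, severity and relatedness in Tables 14.3.1.1 to 14.3.1.4.

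Most of this stands, and it rules out some stronger readings. A reader might infer that the planned output cannot show whether any eye met the criterion, or that averaging conceals a single high eye. The maximum row and the listing contradict both. A reader might also infer that the 30 mm item conflicts with the 25 mm Hg limit. The documents do not support that: the first is a check before the subject goes home on the day of injection, the second a safety criterion over follow-up. Nor can one Day 0 reading establish persistence.

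The reply does not supply a count. The listing offers hand review under an undefined term. Adverse event tables count what investigators chose to report, not eyes beyond stated limits. SAP Appendices A and B let tables be reorganised during programming, but that is no substitute for a derivation. The protocol's qualifier of clinical significance does remain a matter of judgement, so a threshold count would not by itself measure the full criterion.

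**Conclusion.** The concern holds as a gap in the planned derivation and tabulation; the data themselves are collected. The SAP specifies no count of eyes meeting either limit, leaves *persistent* undefined, and omits Day 0 from the pressure tables. Those tables cannot give the number of eyes ever affected once a limit is crossed at more than one visit, and they cannot show persistence. In the constructed example the same tables are compatible with 1 eye ever and 1 persistently affected, or with 4 ever and 0 persistently.

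The example is invented to show what is possible and does not predict what the trial found. The enumeration rests on the assumed range and whole-number recording. If no eye crosses a limit at any tabulated visit, the practical loss is confined to Day 0. The point should be corrected because it concerns a numerically defined criterion under the primary objective, but it does not threaten the study's conclusions as a whole.

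**What to change.** In SAP 10.7.2 and Tables 14.3.4.8.1 and 14.3.4.8.2:

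- Add, by dose and in total, the number and percentage of study eyes and non-study eyes with (i) IOP above 25 mm Hg, (ii) an increase of more than 10 mm Hg from baseline, and (iii) either. Give each at any post-injection visit and persistently.
- State an analysis definition of *persistent* before database lock. Consecutive scheduled visits with a stated minimum interval is one example. Consecutive visits alone would be uneven: Day 1 and Day 2 are one day apart, Month 6 (Day 180) and Month 9 (Day 270) are 90 days apart. The choice is the sponsor's.
- Label these as numeric-threshold counts and keep them separate from the investigator's judgement of clinical significance.
- Add the Day 0 post-injection value and its change as the first post-baseline row.
- Flag qualifying readings in Listing 16.2.8.16.

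The cost is a few table rows, a derived flag and one definition to agree. The counts may look less favourable than means, and the upper limits above show that a zero in a single dose column would say little. No change to data collection or to the conduct of the study is needed.

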10.7.3 B-scan

B-scan results will be tabulated by Normal and Abnormal results at each time point and overall results will be counted as good or poor. B-scan results will also be tabulated by whether injected cells were visualized. If Clinically Significant value is not reported in the follow-up visit, then the value will be imputed based on the value of previous visit, consistent with CRF completion guidelines. For example, if abnormal change from previous visit is "NO" then imputed value will be value from the previous visit.

10.7.4 Dilated Fundoscopic Examination

Dilated Fundoscopic Examination- for the vitreous exam, optic nerve exam, macula exam, and peripheral retina exam, counts and percentages of Normal, Abnormal NCS and Abnormal CS will be presented by eye and time point. When available, summaries of Severity (Mild +1, Moderate +2, Severe +3, Very Severe +4) will also be included. If Clinically Significant value is not reported in the follow-up visit, then the value will be imputed based on the value of previous visit, consistent with CRF completion guidelines. For example, if abnormal change from previous visit is "NO" then imputed value will be value from the previous visit.

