1.0 INTRODUCTION

1.1 Background

1.1.1 Retinitis Pigmentosa

Retinitis pigmentosa (RP) refers to a group of inherited diseases causing retinal degeneration. The cell-rich retina lines the back inside wall of the eye. It is responsible for capturing images from the environment. People with RP experience a gradual decline in their vision because photoreceptor cells (rods and cones) die. Forms of RP and related diseases include Usher syndrome, Leber's congenital amaurosis, rod-cone degeneration, Bardet-Biedl syndrome, and Refsum disease, among others.

In most forms of RP, rods are affected first. Because rods are concentrated in the outer portions of the retina and are triggered by dim light, their degeneration affects peripheral and night vision. When the more centrally located cones - responsible for color and sharp central vision - become involved, the loss is in color perception and central vision. Night blindness is one of the earliest and most frequent symptoms of RP.

RP is typically diagnosed in adolescents and young adults. The classic clinical sign of the disease is the presence of dark deposits in the retina. The main risk factor is a family history of retinitis pigmentosa. It is an uncommon condition affecting about 1 in 4,000 people or roughly 100,000 individuals in the US¹. Cases of RP are associated with a wide variety of known gene mutations, with new mutations still being discovered. The mutations can be inherited from one or both parents, or occur spontaneously; the pattern of inheritance can be autosomal recessive, autosomal dominant, X-linked or mitochondrial.

There is no effective treatment for RP; once photoreceptors are lost, they do not regenerate. The rate of deterioration of vision varies from person to person, with most people with RP legally blind by age 40. People with RP also often develop cataracts at an early age, or swelling of the retina (retinal edema). Numerous breakthroughs in the treatment of cataract and corneal disease have greatly decreased the incidence of blindness from these causes. In contrast, treatment of retinal and optic nerve disease is more limited, with these conditions now representing major causes of incurable visual loss and a significant unmet medical need.

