3.3 Study Duration

The overall duration of the study is anticipated to be approximately 2 years. The study will be considered to have started when the first site is initiated. The study will be considered to have finished after the last subject has completed the last follow-up visit in the study (12 months following treatment).

All subjects who receive jCell treatment will be closely monitored throughout the observation period. All subjects who receive treatment with jCell will be encouraged to participate in a follow-on study to assess potential long term effects (safety and efficacy) of jCell treatment. The follow-on study is planned to include an at least two years of additional subject monitoring; additional follow up visits will be scheduled at least every 6 months with

monitoring to include medical history and physical exam, vital signs, safety lab tests (as at other visits), urinalysis, adverse events, BCVA and slit lamp/fundus exam at each visit; and additional ophthalmic exams at specified visits. More frequent visits will be scheduled during the initial or follow-on study as appropriate should this be indicated by safety concerns.

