n	n	n	n	n	n
Mean (SD)	$\mathbf{x}\mathbf{x}.\mathbf{x}(\mathbf{x}\mathbf{x}.\mathbf{x})$	xx.x (xx.x)	xx.x (xx.x)	xx.x(xx.x)	xx.x (xx.x)
Median	XX X	XX X	XX X	XX X	XX X
Min Max	XX XX	XX XX	XX XX	VV VV	XX XX
Ivini, ivian	лл, лл	лл, лл	лл, лл	ΔΛ, ΔΛ	лл, лл

^[1] Total includes both Cohorts 1 and 2.

^[2] Baseline is defined as the value obtained at the baseline visit. If the baseline value is missing, the baseline value will be the last non-missing value recorded prior to the first dose of study drug. path/t_program.sas date time

Programmer Note: Continue table for Visits: Day 3, Day 7, Day14, Day 21, Day 28, Month 2, Month 3, Month 4, Month 5, Month 6, Month 9, Month 12 or Early Term. Programmer Note: Table 14.2.1.2 will contain the same information for the Non-Study Eye
jCyte, Inc. Protocol: JC-01

	Cohort	1	Cohor	t 2	
	0.5 x 10 ⁶ hRPC (N=)		0.5 x 10 ⁶ hRPC (N=)		Total ^[1] (N=)
Proportion of Subjects with Specified increase in letters correct for any Post	(n=)	(n=)	(n=)	(n=)	(n=)
Baseline Assessment					
>=5 Letters Increase	n (%)	n (%)	n (%)	n (%)	n (%)
>=10 Letters Increase	n (%)	n (%)	n (%)	n (%)	n (%)
>=15 Letters Increase	n (%)	n (%)	n (%)	n (%)	n (%)
Proportion of Subjects with Specified increase in letters correct at Month 3	(n=)	(n=)	(n=)	(n=)	(n=)
>=5 Letters Increase	n (%)	n (%)	n (%)	n (%)	n (%)
>=10 Letters Increase	n (%)	n (%)	n (%)	n (%)	n (%)
>=15 Letters Increase	n (%)	n (%)	n (%)	n (%)	n (%)
Proportion of Subjects with Specified increase in letters correct at Month 6	(n=)	(n=)	(n=)	(n=)	(n=)
>=5 Letters Increase	n (%)	n (%)	n (%)	n (%)	n (%)
>=10 Letters Increase	n (%)	n (%)	n (%)	n (%)	n (%)
>=15 Letters Increase	n (%)	n (%)	n (%)	n (%)	n (%)
Proportion of Subjects with Specified increase in letters correct at Month 9	(n=)	(n=)	(n=)	(n=)	(n=)
>=5 Letters Increase	n (%)	n (%)	n (%)	n (%)	n (%)
>=10 Letters Increase	n (%)	n (%)	n (%)	n (%)	n (%)
>=15 Letters Increase	n (%)	n (%)	n (%)	n (%)	n (%)
Proportion of Subjects with Specified increase in letters correct at Month 12 or Eartly Termination	(n=)	(n=)	(n=)	(n=)	(n=)
>=5 Letters Increase	n (%)	n (%)	n (%)	n (%)	n (%)
>=10 Letters Increase	n (%)	n (%)	n (%)	n (%)	n (%)
>=15 Letters Increase	n (%)	n (%)	n (%)	n (%)	n (%)
ludes both Cohorts 1 and 2.					

^[1] Total in path\t_program.sas date time

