Programmer Note: Continue table for Visits: Day 7, Month3, Month 6, Month 12/Early Term. Programmer Note: Table 14.3.4.9.2 will contain the same information for the Non-Study Eye.

Programmer Note: Denominators used for percentage calculation to be based on number of results reported for that perticular time point.

jCyte, Inc. Protocol: JC-01

	Cohort 1		Cohort 2		
	0.5 x 10 ⁶ hRPC		0.5 x 10 ⁶ hRPC		Total ^[1]
	(N=)		(N=)		(N=)
Vitreous Examination					
Baseline ^[2]	(n=)	(n=)	(n=)	(n=)	(n=)
Mild +1	n (%)	n (%)	n (%)	n (%)	n (%)
Moderate +2	n (%)	n (%)	n (%)	n (%)	n (%)
Severe +3	n (%)	n (%)	n (%)	n (%)	n (%)
Very Severe +4					
Normal	n (%)	n (%)	n (%)	n (%)	n (%)
Abnormal, Not Clinically Significant	n (%)	n (%)	n (%)	n (%)	n (%)
Abnormal, Clinically Significant	n (%)	n (%)	n (%)	n (%)	n (%)
Day 1	(n=)	(n=)	(n=)	(n=)	(n=)
Mild +1	n (%)	n (%)	n (%)	n (%)	n (%)
Moderate +2	n (%)	n (%)	n (%)	n (%)	n (%)
Severe +3	n (%)	n (%)	n (%)	n (%)	n (%)
Very Severe +4					
Normal	n (%)	n (%)	n (%)	n (%)	n (%)
Abnormal, Not Clinically Significant	n (%)	n (%)	n (%)	n (%)	n (%)
Abnormal, Clinically Significant	n (%)	n (%)	n (%)	n (%)	n (%)
Day 2	(n=)	(n=)	(n=)	(n=)	(n=)
Mild +1	n (%)	n (%)	n (%)	n (%)	n (%)
Moderate +2	n (%)	n (%)	n (%)	n (%)	n (%)
Severe +3	n (%)	n (%)	n (%)	n (%)	n (%)
Very Severe +4					
Normal	n (%)	n (%)	n (%)	n (%)	n (%)
Abnormal, Not Clinically Significant	n (%)	n (%)	n (%)	n (%)	n (%)
Abnormal, Clinically Significant	n (%)	n (%)	n (%)	n (%)	n (%)

Table 14.3.4.10.1Dilated Fundoscopic Examination: Study EyeSafety Population

^[1] Total includes both Cohorts 1 and 2.

^[2] Baseline is defined as the value obtained at the baseline visit. If the baseline value is missing, the baseline value will be the last non-missing value recorded prior to the first dose of study drug. path/t program.sas date time

Programmer Note: Continue table for Optic Nerve, Macula, and Peripheral Retina Examinations.

Programmer Note: Continue table for Visits: Day 3, Day 7, Day 14, Day 21, Day 28, Month 2, Month 3, Month 4, Month 5, Month 6, Month 9, Month 12/Early Term.

Programmer Note: Table 14.3.4.10.2 will contain the same information for the Non-Study Eye. Programmer Note: Denominators used for percentage calculation to be based on number of results reported for that perticular time point.

jCyte, Inc. Protocol: JC-01

	Cohort	Cohort 1		Cohort 2	
	0.5 x 10 ⁶ hRPC		0.5 x 10 ⁶ hRPC		Total ^[1]
	(N=)		(N=)		(N=)
Day0	(n=)	(n=)	(n=)	(n=)	(n=)
Injected eye examined					

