		Day 7	Date9.(xx)	Time5.	Yes/No/NA	Yes/No/NA	Abnormal CS:Abnormalit y	Yes/No/NA	Irregular Posterior detachment	Good/Poor	Abnormal CS:Abnorm ality	Yes/No/NA	Irregular Posterior detachment	Good/Poor
		Month 3	Date9.(xx)	Time5.	Yes/No/NA	Yes/No/NA	Abnormal NCS	Yes/No/NA		Good/Poor	Abnormal NCS	Yes/No/NA		Good/Poor
		Month 6	Date9.(xx)	Time5.	Yes/No/NA	Yes/No/NA	Normal	Yes/No/NA		Good/Poor	Normal	Yes/No/NA		Good/Poor
		Month 12 o Early Termination	or Date9.(xx)	Time5.	Yes/No/NA	Yes/No/NA	Normal	Yes/No/NA		Good/Poor	Normal	Yes/No/NA		Good/Poor
		i erminatio												
Cohort 1 - 0.5 x 10^6 hRPC	XXXXXX	Baseline	Date9.(xx)	Time5.	Yes/No/NA	Yes/No/NA	Normal	Yes/No/NA		Good/Poor	Normal	Yes/No/NA		Good/Poor
		Day 3	Not done: Reason											
		Day 7	Date9.(xx)	Time5.	Yes/No/NA	Yes/No/NA	Abnormal CS:Abnormalit v	Yes/No/NA		Good/Poor	Abnormal CS:Abnorm ality	Yes/No/NA		Good/Poor
		Month 3	Date9.(xx)	Time5.	Yes/No/NA	Yes/No/NA	Abnormal NCS	Yes/No/NA		Good/Poor	Abnormal NCS	Yes/No/NA		Good/Poor
		Month 6	Date9.(xx)	Time5.	Yes/No/NA	Yes/No/NA	Normal	Yes/No/NA		Good/Poor	Normal	Yes/No/NA		Good/Poor
		Month 12 o Early Termination	or Date9.(xx)	Time5.	Yes/No/NA	Yes/No/NA	Normal	Yes/No/NA		Good/Poor	Normal	Yes/No/NA		Good/Poor

Note: CS=Clinically Significant, NCS=Not Clinically Significant.

path\l_program.sas date time

Programmer Note : If B-Scan measurement was not completed, please display "Not Done" and the reason in the "Measurement Date/Time" column. Programmer Note Include description of abnormality and Clinically Significant information in "B-Scan Result" column.

Listing 16.2.8.18 Dilated Funduscopic Examination Part 1 of 4

						OD (Right)						
Treatment Group	Subject ID	Visit	Time of Dilator Administrat ion	Examination Date (Study Day)	Time of Examination	Vitreous Exam Results	If Abnormal, Change from Previous Visit?	Vitreous Exam Severity	Optic Nerve Exam	If Abnormal, Change from Previous Visit?	Optic Nerve Exam Severity	
Cohort 1 - 0.5 x 10 ⁶ hRPC	XXXXXX	Screening	Time5.	Date9. (xx)	Time5.	Normal		Mild	Normal		Mild	
		Baseline	Time5.	Date9. (xx)	Time5.	Not Done		Moderate	Not Done		Moderate	
	•••••	Day 1	Time5.	Date9. (xx)	Time5.	Abnormal CS: Abnormality	Yes	Severe	Abnormal CS: Abnormality	Yes	Severe	
		Day 2	Time5.	Date9. (xx)	Time5.	Abnormal NCS	No	Very Server	Abnormal NCS	No	Very Server	
		Day 3	Time5.	Date9. (xx)	Time5.	Normal		Mild	Normal		Mild	
		Day 7	Time5.	Date9. (xx)	Time5.	Not Done		Moderate	Not Done		Moderate	

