10 IIKFC

Note: With respect to "Vitreous Exam", "Optic Nerve Exam", "Macula Exam", and "Peripheral Retina Exam" columns, CS=Clinically Significant, NCS=Not Clinically Significant. path\l program.sas date time

Programmer Note: Sorting order is by Cohort #, subject ID, examination date (include unscheduled visits in the date sequence), and examination time.

Programmer Note: If dilated funduscopic examination was not performed, please display "Not Done" and the reason in the "Examination Date/Time" column

This page intentionally left blank

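### The by-visit ophthalmic exam tables have no row for unscheduled examinations and no any-time worsening count, so some new findings would appear only in listings and AE tables

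*SAP*

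**What the plan says.** **Extra visits.** Protocol 3.3 provides that "More frequent visits will be scheduled during the initial or follow-on study as appropriate should this be indicated by safety concerns".

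**What is tabulated.** For the vitreous, optic nerve, macula and peripheral retina, SAP 10.7.4 states that "counts and percentages of Normal, Abnormal NCS and Abnormal CS will be presented by eye and time point", and adds a four-level severity grade when one is available. The programmer note to Table 14.3.4.10.1 reads "Continue table for Visits: Day 3, Day 7, Day 14, Day 21, Day 28, Month 2, Month 3" and runs on to Month 12 or early termination. The slit-lamp (14.3.4.6), B-scan (14.3.4.9) and OCT (14.3.4.12) shells are also built from named visits. None has an unscheduled, shift or worst-post-baseline row.

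**Where unscheduled visits appear.** The SAP mentions them only in a sort note to Listing 16.2.8.18: "Sorting order is by Cohort #, subject ID, examination date (include unscheduled visits in the date sequence), and examination time".

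**Change item.** The fundoscopic listing carries a column "If Abnormal, Change from Previous Visit". For this exam the item is listed and is used to carry forward a missing clinical-significance code, but no table counts it.

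**Baseline state of the eye.** Protocol 1.1.1 says: "The classic clinical sign of the disease is the presence of dark deposits in the retina".

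**Vision gains.** Table 14.2.1.3 has a block headed "Proportion of Subjects with Specified increase in letters correct for any Post" baseline assessment, which is an any-time count.

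**Named safety criteria.** Protocol 3.2.2 lists epiretinal membrane, retinal detachment, neovascularization and endophthalmitis. None has its own row in a SAP 10.7 table.

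**The concern.** Safety and tolerability are the primary objective. An examination made because something seemed wrong is among the most likely to show harm to the injected eye, yet the by-visit exam tables have nowhere to put it. The retina in RP can also be abnormal before injection. A table of how many eyes are abnormal at each visit therefore says little about how many eyes acquired something new. If neither route to a new finding is summarised per eye, the comparison of injected with fellow eye, which the two-eye layout is meant to support, can look flat when it is not.

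**Working it through.** The plan has no figure to reproduce here: SAP section 4 gives no formal basis for the sample size. The cell sizes follow from the design: 4 + 4 + 3 + 3 = 14 per cohort, and 2 × 14 = 28.

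**Step 1: gaps in which a finding can come and go.** Nominal days are from protocol section 7.5 and the exam schedule from protocol Table 2. Month 12 is taken as Day 365, which is an assumption.

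- Slit lamp and fundus, from Day 28 (28, 60, 90, 120, 150, 180, 270, 365): gaps of 32, 30, 30, 30, 30, 90 and 95 days. With the ±4-day windows, Month 6 to Month 9 can reach (270 + 4) − (180 − 4) = 98 days.
- B-scan, from Day 7 (7, 90, 180, 365): gaps of 83, 90 and 185 days.
- OCT, from Day 28 (28, 90, 180, 270, 365): gaps of 62, 90, 90 and 95 days.

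The protocol's visit lists disagree with Table 2 in two places, which need reconciling. The Month 5 list omits the slit-lamp and fundus exam; without it that gap is 180 − 120 = 60 days. The Month 9 list omits OCT; without it that gap is 365 − 180 = 185 days.

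**Step 2: what one affected eye does to a four-eye cell.** The baseline states are hypothetical.

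| Case | Baseline | After one eye changes | By-visit count |
|---|---|---|---|
| A. New retinal finding, same category and grade | 4 CS, all +2 | 4 CS, all +2 | Unchanged |
| B. Grade rises | 4 CS, all +2 | 4 CS; one +3, three +2 | Severity row moves |
| C. NCS becomes CS | 4 NCS | 3 NCS, 1 CS | Moves |
| D. Vitreous or B-scan normal at baseline | 4 Normal | 3 Normal, 1 CS | Moves |
| E. Seen at an unscheduled exam, gone by the next scheduled one | 4 Normal | 4 Normal | Unchanged |

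A new epiretinal membrane without CME could be case A, because the OCT table counts only CME and foveal involvement.

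**Step 3: what an any-time row would show.** One affected eye prints as 1/4 = 25.0% (exact 95% CI 0.6 to 80.6), 1/3 = 33.3% (0.8 to 90.6), or 1/28 = 3.6% (0.1 to 18.3) over all subjects.

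**Step 4: where cases A and E would still be seen.** Both reach the listings. If reported as AEs, both also add an event to the TEAE tables, which are not organised by visit.

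**The case against.** The strongest reply is that AE reporting covers the gap. Protocol 9.1 makes a condition newly detected after injection an AE. SAP 10.2 counts TEAEs whatever the visit, and its maximum-severity table is in effect a worst-ever summary. A visit added for a safety concern is also where an AE is likely to be recorded. A reader might infer that a new finding leaves every count in the report unchanged, or that gains are counted at any time while harms never are. The documents do not support either reading, because a reported finding enters the TEAE tables. The contrast with the BCVA gain block holds only among the exam tables.

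AE reporting is still not a full answer. Protocol 8.1.5 says these procedures are there to pick up eye AEs that ordinary AE collection could miss. Protocol 9.1 excludes expected RP progression unless it is worse than expected, so a retinal change needs a judgement before it becomes an AE. Table 14.3.1.1 has no split by eye, and Listing 16.2.7.1 has no eye column, so laterality depends on the verbatim term.

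Other points narrow the concern and stand:

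- The fundoscopic table has three levels plus severity, so cases B and C register.
- CME at a scheduled OCT visit, leakage or ischemia on angiography, and specific vitreous appearances are counted directly. The vitreous table (14.3.4.11) also has a row for change from the previous exam.
- Baseline abnormality is supported for the retina only, not for the vitreous, optic nerve or B-scan.
- The SAP has no rule excluding unscheduled exams, and it allows table layouts to be changed during programming.
- With three or four eyes per cell, a careful reader can work from the listings.

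**Conclusion.** The point holds in a limited form. As specified, the slit-lamp, fundoscopic, B-scan and OCT tables have no place for unscheduled exams and no per-eye summary of new or worsened findings. Cases A and E leave their by-visit counts unchanged; cases B, C and D do not.

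For an affected eye in case A, the table shows 4/4 before and after where an any-time row would show 1/4. Case E can occur in gaps of up to about 95 days for fundus exams and 185 days for B-scan.

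This rests on three assumptions: that programmers follow the shells as written; that in case A the retina is already coded Abnormal CS at the same grade; and that Month 12 falls at Day 365. The documents give no baseline rate of Abnormal CS, so how often case A would arise cannot be estimated. The data would still be in the database and listings. This is a weakness in the summary of the primary objective, not a loss of safety information.

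**What to change.** Keep the by-visit tables. Add to the fundoscopic, slit-lamp, B-scan and OCT tables, separately for study and non-study eye, one row: *new or worsened versus baseline at any post-injection examination, scheduled or unscheduled, n/N injected*.

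Count an eye if any of these holds:

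- its category shifts from baseline (Normal to Abnormal, or NCS to CS);
- its severity grade rises, where a grade is recorded (the B-scan shell has none);
- CME or foveal involvement is present that was absent at baseline.

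The change item cannot be used alone. It is Yes/No, is asked only when the result is abnormal, refers to the previous visit and has no direction, so an improvement also reads as Yes. Where an eye is already abnormal and the item is Yes, classify the change as new, worsened or improved from the recorded abnormality or pathology text before database lock. Confirm also that CME is recorded by eye, since Listing 16.2.6.3 shows a single CME column while the tables are by eye.

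The cost is a SAP text change, a small amount of programming and a short data review before lock. No new data collection is needed.
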